2. OBJECTIVES AND ENDPOINTS

2.1. Objectives

The primary objectives of the study are:

- to assess the effect of food on the PK of LOXO-305 administered under fasted conditions and after a standard meal in healthy adult subjects
- to assess the effect of a gastric pH change on the PK of LOXO-305 after multipledoses of a PPI (omeprazole) in healthy adult subjects

The secondary objective of the study is:

• to determine the safety and tolerability of a single dose of LOXO-305 administered with and without food and in the presence of a PPI (omeprazole) in healthy adult subjects

2.2. Endpoints

The following PK parameters will be calculated whenever possible, based on the plasma concentrations of LOXO-305 (as appropriate):

- area under the concentration-time curve from Hour 0 to 24 hours postdose, as calculated by the linear trapezoidal method (AUC₀₋₂₄)
- area under the concentration-time curve from Hour 0 to the last measurable concentration (AUC_{0-t})
- area under the concentration-time curve extrapolated to infinity (AUC_{0-inf})
- extrapolation for area under the concentration-time curve (%AUC_{extrap})
- maximum observed plasma concentration (C_{max})
- time to maximum observed concentration (t_{max})

- apparent terminal elimination rate constant (λ_Z)
- apparent systemic clearance (CL/F)
- apparent terminal elimination half-life $(t_{1/2})$.

No value for AUC_{0-inf} , CL/F, or $t_{\frac{1}{2}}$ will be reported for cases that do not exhibit a terminal log linear phase in the concentration-time profile.

No PK parameters will be calculated for subjects with 2 or fewer consecutive timepoints with quantifiable concentrations.

Individual and mean plasma concentration-time curves (both linear and log linear) will be included in the final report.

Safety and tolerability will be assessed by monitoring AEs, performing physical examinations and clinical laboratory tests, measuring vital signs, and 12-lead ECGs.

3. INVESTIGATIONAL PLAN

3.1. Overall Study Design and Plan

This is a Phase 1, open-label, randomized, 2-way crossover, 3-period study. A single oral dose of LOXO-305 will be administered under fasted conditions (Treatment A) and fed conditions (Treatment B). Multiple oral doses of omeprazole will be administered once daily from Day 15 through Day 18, with a single oral dose of LOXO-305 co-administered with omeprazole under fasted conditions on Day 18 (Treatment C). PK sampling will be obtained for 168 hours after administration of each dose of LOXO-305 (ie, on Days 1, 8, and 18). The 2 treatment sequences will be ABC and BAC. Subjects will be randomly assigned to 1 of the 2 treatment sequences, according to a randomization scheme issued by Covance.

In Treatment A, a single oral dose of 200 mg LOXO-305 will be administered in the morning on Day 1 or Day 8 (according to the randomization scheme), following a fast of at least 10 hours prior to and 4 hours after dosing. In Treatment B, a single oral dose of 200 mg LOXO-305 will be administered in the morning on Day 1 or Day 8 (according to the randomization scheme), approximately 30 minutes after starting a standard breakfast. In Treatment C, a single oral dose of 40 mg omeprazole will be administered in the morning on Days 15, 16 and 17, following a fast of at least 8 hours prior to omeprazole dosing, followed by a standard breakfast administered approximately 1 hour after dosing. On Day 18, a single oral dose of 40 mg omeprazole will be co-administered with a single oral dose of 200 mg LOXO-305 in the morning, following a fast of at least 10 hours prior to and 4 hours after omeprazole and LOXO-305 co-administration. Standard breakfasts should be entirely consumed within 30 minutes. Serial PK blood samples for the analysis of plasma concentrations of LOXO-305 will be collected from predose through 168 hours postdose for each treatment.

There will be a washout period of 7 days between the doses of LOXO-305 administered in Treatments A and B, and a washout period of 7 days between the doses of LOXO-305 administered in Treatments A or B and the first dose of omeprazole in Treatment C.

To assess their eligibility to enter the study, potential subjects will be screened within 28 days (Days -29 to -2) and be admitted to the Clinical Research Unit (CRU) on Day -1 (Check-in). Replacement subjects may be enrolled only if deemed necessary by the Sponsor.

Subjects will be confined at the CRU from the time of Check-in (Day -1) until End of Treatment (EOT) on Day 25 upon completion of all PK and safety assessments or Early Termination (ET) if the subject discontinues. A follow-up phone call will occur for all subjects who received at least 1 dose of study drug (including subjects who are terminated early) 7 days (\pm 2 days) after EOT or ET.

The start of the study is defined as the date the first subject who is enrolled in the study signs an Informed Consent Form (ICF). Note that enrolled subjects are defined as those subjects who are assigned a dose of study drug; this definition excludes screen failure subjects.

In this study, physical examinations, 12-lead ECGs, vital signs, How Do You Feel? (HDYF?) inquiries, clinical chemistry panel, coagulation parameters, creatine kinase (CK), complete blood count (CBC), urinalysis (UA; Appendix 2) and recording of concomitant medications will be performed at specified times during the study (for specific timepoints and details on each study variable, refer to Appendix 4). Adverse events and SAEs will be collected beginning at informed consent. Adverse events will be reported throughout the study (ie, from signing of the ICF until End of Study [EOS], or until ET if the subject discontinues from the study and does not complete a follow-up phone call), either as subject medical history (if the event is reported as beginning prior to signing of the ICF or if the event occurs prior to study drug administration on Day 1 and is assessed as not related to study procedures by the Investigator [or designee]) or as AEs (if the event occurs after signing of the ICF but prior to study drug administration on Day 1 and is assessed as related to study procedures by the Investigator [or designee], or if the event occurs after study drug administration on Day 1 through EOT or ET regardless of relationship to study drug). From EOT or ET through EOS, only AEs assessed as related to study drug by the Investigator (or designee) are to be reported. All SAEs that develop from the time of ICF signing until EOS (or ET, if the subject discontinues from the study and does not complete a follow-up phone call) are to be reported. Study completion is defined as the time of the last subject's follow-up phone call.

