4.6. Removal of Subjects from Study Participation

Subjects will be informed that they are free to withdraw from the study at any time and for any reason. The Investigator (or designee) may remove a subject from the study if, in the Investigator's (or designee's) opinion, it is not in the best interest of the subject to continue the study. Subjects may be withdrawn because of the following: change in compliance with inclusion/exclusion criterion that is clinically relevant and affects subject safety, occurrence of AEs, occurrence of pregnancy, intake of non-permitted concomitant medication that might affect subject safety or study assessments/objectives, etc. Notification of withdrawal will immediately be made to the Study Monitor. In case of withdrawal, efforts will be made to perform all final study day assessments (Appendix 4). The date the subject is withdrawn from the study and the reason for withdrawal will be recorded on the subject's electronic Case Report Form (eCRF). All withdrawn subjects with AEs that are assessed as related to study drug and which are ongoing at ET may continue to be followed until the symptoms or value(s) return to normal, or acceptable levels, as judged by the Investigator (or designee) and confirmed by the Sponsor.

The entire study may be discontinued at the discretion of the Investigator (or designee) or Sponsor, based on the occurrence of the following:

- adverse events unknown to date with respect to their nature, severity, and/or duration;
- increased frequency and/or severity and/or duration of known AEs;
- medical or ethical reasons affecting the continued performance of the study;
- difficulties in the recruitment of subjects;
- cancellation of drug development.

In the event that the study is terminated early, the Sponsor or its designee will provide specific guidance to the CRU regarding the EOS procedures.

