Unless a subject withdraws consent or is withdrawn from the study and does not complete the follow-up phone call, all subjects must be followed until EOS. Subjects with AEs that are assessed as related to study drug by the Investigator (or designee) which are ongoing at EOS may continue to be followed until the symptoms or value(s) return to normal, or acceptable levels, as judged by the Investigator or designee and confirmed by the Sponsor. The Investigator (or designee) should use appropriate judgment in ordering additional tests as necessary to monitor the resolution of events. The Sponsor may request that additional safety tests be performed.

Subjects will receive a follow-up phone call 7 days (\pm 2 days) after EOT or ET to determine if any SAE or drug-related AE has occurred since the EOT or ET visit.

At all times, a subject may be required to remain at the CRU for longer at the discretion of the Investigator (or designee).

Any event that meets the criteria of a suspected unexpected serious adverse reaction (SUSAR) will be reported to the Institutional Review Board (IRB) according to CRU policy by the Investigator (or designee) and to regulatory authorities by the Sponsor (or Sponsor designee) according to regulatory authority requirements. Refer to Reference Safety Information in the current IB¹ for LOXO-305 for expected adverse reactions.

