- v. EOT is defined as when the subject is released from the CRU following completion of all assessments through Day 25. ET is defined as when the subject is released from the CRU if the subject terminates the study early. Vital signs, ECG, and safety laboratory results for clinical chemistry, hematology, coagulation, and UA are to be available for review by the Investigator or designee prior to subject release from the CRU at the EOT or ET visit.
- w. To be performed 7 days (± 2 days) following EOT or ET. EOS is defined as when the CRU contacts the subject by a follow-up phone call 7 days (± 2 days) after the EOT visit or ET visit to determine if any SAE or study drug-related AE has occurred since the EOT or ET visit. All subjects who received LOXO-305 (including subjects who are terminated early) will be contacted.

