8.6. Safety and Tolerability Assessments

8.6.1. Adverse Events

All AEs will be coded using the Medical Dictionary for Regulatory Activities (MedDRA) Version 22.1. All AEs will be assigned severity grade using National Cancer Institute Common Terminology Criteria for Adverse Events (CTCAE) Version 5.0.

A treatment-emergent adverse event (TEAE) will be defined as an AE that starts during or after the first dose, or starts prior to the first dose and increases in severity after the first dose.

A treatment-related TEAE will be defined as a TEAE with a relationship of related to the study treatment (LOXO-305 or Omeprazole), as determined by the investigator.

The assignment of TEAEs to the associated treatments will be as follows:

- A TEAE occurring during or after Day 1 dosing and prior to Day 8 dosing will be assigned to '200 mg LOXO-305 (Fasted)' or '200 mg LOXO-305 (Fed)' depending on the subject's fasting status prior to Day 1 dosing.

- A TEAE occurring during or after Day 8 dosing and prior to Day 15 dosing will be assigned to '200 mg LOXO-305 (Fasted)' or '200 mg LOXO-305 (Fed)' depending on the subject's fasting status prior to Day 8 dosing.
- A TEAE occurring during or after Day 15 dosing and prior to Day 18 dosing will be assigned to '40 mg Omeprazole (Fasted)'.
- A TEAE occurring during or after Day 18 dosing will be assigned to '200 mg LOXO-305 + 40 mg Omeprazole (Fasted)'.

All AEs will be listed. In addition to the data recorded in the database, the listings will include derived onset time and duration. Onset time will be calculated from the time of the last dose for TEAEs only.

The frequency of subjects with TEAEs and the number of TEAEs will be summarized for the following categories:

- TEAEs (overall, serious, and leading to discontinuation) by treatment
- TEAEs by severity and treatment
- Treatment-related TEAEs (overall, serious, and leading to discontinuation) by treatment
- Treatment-related TEAEs by severity and treatment

The frequency of subjects will be summarized separately for TEAEs and treatment-related TEAEs by the following:

- System organ class, preferred term, and treatment
- Preferred term and treatment
- System organ class, preferred term, day of onset, and treatment

For the AE data the following rules will apply:

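### After early release, non-serious AEs judged unrelated go unreported, so a withdrawn subject's all-causality TEAE window can fall well short of the 168 hours that completers get

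*Protocol*

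**What the plan says.** Protocol 3.1 sets a broad window first. An event counts as an AE "or if the event occurs after study drug administration on Day 1 through EOT or ET regardless of relationship to study drug". After that point a filter applies: "From EOT or ET through EOS, only AEs assessed as related to study drug by the Investigator (or designee) are to be reported". Serious events are exempt from the filter: "All SAEs that develop from the time of ICF signing until EOS" are reportable, except that reporting stops at ET for a discontinued subject who does not complete the follow-up call. The same rule appears in Protocol 7.2.1, Appendix 4 footnote i and SAP Section 4.

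Appendix 4 footnote v fixes the cut-off for withdrawn subjects: "ET is defined as when the subject is released from the CRU if the subject terminates the study early". No minimum stay after a dose is given. Protocol 7.2.1 lets the investigator keep a subject longer, and Protocol 4.6 promises only best efforts at final assessments. For AEs still running at withdrawal, Protocol 4.6 names related events only: "All withdrawn subjects with AEs that are assessed as related to study drug and which are ongoing at ET may continue to be followed".

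Every dosed subject, including early leavers, is called 7 ± 2 days after EOT or ET. Protocol 7.2.1 gives the purpose of that call: "to determine if any SAE or drug-related AE has occurred since the EOT or ET visit".

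SAP 8.6.1 then summarises "TEAEs (overall, serious, and leading to discontinuation) by treatment", with no adjustment for observation time and no split by completion status.

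**The concern.** One cut-off serves two different groups. For a completer it falls on Day 25, a week after the last LOXO-305 dose. For a withdrawn subject it falls whenever that subject leaves, which may be hours after a dose. Take a non-serious event, judged unrelated, that starts 30 hours after dosing. In a completer it is a TEAE; in a subject released at 24 hours it is not recorded. Both subjects sit in the same treatment column.

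The causality filter does not cleanly remove only irrelevant events. Under Appendix 1, a related event needs a compatible time course and no other identifiable cause. The study is open-label. The restrictions on medication, alcohol and caffeine (Protocol 6.1 and 6.2) end at EOT or ET, so other causes become easier to name after release. All-causality tables avoid reliance on that judgement, and for early leavers the protection ends at the door.

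At stake is the secondary objective, safety and tolerability, which is analysed descriptively. AEs are a listed reason for withdrawal (Protocol 4.6), so the shortened windows may fall on informative subjects. SAP 8.1.1 and 8.1.2 also drop ET measurements from summary statistics, which leaves the AE tables carrying more of these subjects' safety information.

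**Working it through.** **Completers' window.** Doses and EOT are from Protocol 3.1 and Appendix 4. Day 18 to Day 25: (25 − 18) × 24 = 168 h, matching the figure in Appendix 4 footnotes e and f. Day 1 to Day 8: (8 − 1) × 24 = 168 h. Day 8 to Day 15: (15 − 8) × 24 = 168 h. Every LOXO-305 dose therefore has at least 168 h of all-causality collection.

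**Early leavers' window.** The release times t are assumed, since the documents give none. Share = t/168; missing hours = 168 − t. The call is 7 ± 2 days after release, or 120 to 216 h, so it falls between t + 120 and t + 216 h after the dose.

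| Release after dose | Share of 168 h | Hours missing | Call, hours after dose |
|---|---|---|---|
| 4 h | 2.4% | 164 | 124–220 |
| 12 h | 7.1% | 156 | 132–228 |
| 24 h | 14.3% | 144 | 144–240 |
| 72 h | 42.9% | 96 | 192–288 |

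The existing call falls late enough to recover most or all of the missing time.

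**What falls in the gap.** For an event that starts after ET:

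| Event | Call completed | Call not completed |
|---|---|---|
| Serious, any cause | reported | not reported |
| Non-serious, related | reported | not reported |
| Non-serious, unrelated | not reported | not reported |

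**Size.** Let q be the risk of a non-serious unrelated TEAE over 168 h, d the share of subjects leaving, and t the release time. These are assumptions: q = 10–30%, d = 5–10%, t = 4–24 h. With a constant hazard, the risk by release is p = 1 − (1 − q)^(t/168), and the reported incidence of these events for the treatment falls by d × (q − p).

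- Smallest: q = 0.10, t = 24, d = 0.05. p = 1 − 0.90^(24/168) = 0.0149; loss = 0.05 × (0.10 − 0.0149) = 0.43 percentage points.
- Largest: q = 0.30, t = 4, d = 0.10. p = 1 − 0.70^(4/168) = 0.0085; loss = 0.10 × (0.30 − 0.0085) = 2.92 percentage points.

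**Direction.** Let c be the chance that an early leaver has a TEAE linked to leaving, recorded before ET. Leavers show at least the completers' proportion once c ≥ (q − p)/(1 − p). For q = 0.10, t = 24: 0.0851/0.9851 = 0.086. For q = 0.30, t = 4: 0.2915/0.9915 = 0.294. The break-even is about 9% to 29%.

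**The case against.** The best defence is that the gap is narrow and the rule deliberate. It is stated consistently in both documents. What is lost is non-serious, judged unrelated, and starts after release. An AE that causes withdrawal begins before ET, is recorded whatever its cause, and appears in the SAP's category for TEAEs leading to discontinuation. The Appendix 4 grid already marks the open health inquiry (HDYF?) and AEs/SAEs at the follow-up call, so the restriction is on what is then reported. Widening it would also set telephone-recalled events from unrestricted life beside events collected daily in confinement. Safety is secondary, with no inferential analysis.

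Most of this stands, and it limits the point. It does not remove the unequal window. Keeping a subject longer is optional, the related-only filter rests on an open-label judgement, and the tables make no allowance for observation time. The recall problem is real, but flagging those events deals with it.

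A reader might infer that AE collection stops altogether at release. That is true only if the call is not completed. A reader might also infer that TEAE counts are lowest in early leavers, or that a treatment losing subjects must look better tolerated. Neither follows: above the 9–29% break-even, leavers match or exceed completers.

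**Conclusion.** The asymmetry is real and modest. For subjects who terminate early, non-serious AEs judged unrelated that start after release are not reported, although release may come at any time after a dose; completers are covered for at least 168 h after every LOXO-305 dose. Such TEAEs may be under-ascertained, and the by-treatment all-causality tables can be affected. The primary pharmacokinetic analysis is not.

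Under the assumptions above, the loss is about 0.4 to 2.9 percentage points in a treatment's incidence of these events. Actual withdrawals could put it outside that range, and with none it is zero.

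Two other measures are tempting but do not size the gap. One is the drug remaining at release: with the approximate 18 h half-life in Protocol 1.3.2, 2^(−24/18) is about 40% at 24 h. Events judged related are still collected, and that half-life rests on 0 to 8 h sampling in patients. The other is one missed event divided by the number of subjects. That number is not shown, and the figure applies only where the missed event is the subject's sole TEAE on that treatment.

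**What to change.** Amend Protocol 3.1, 7.2.1 and Appendix 4 footnotes i and w, with SAP Section 4 (and the synopsis, which repeats the rule), along these lines: *For subjects who terminate early, all AEs regardless of relationship are recorded through the later of ET and 168 hours after the last dose of any study drug (LOXO-305 or omeprazole), or to the follow-up call if that comes first.* Use the HDYF?/AE inquiry already scheduled at the call. Leave the completers' rule unchanged.

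The anchor must be either study drug. A subject leaving on Days 15 to 17 had LOXO-305 on Day 8, so 168 h from that dose has already passed by the morning of Day 15, and a LOXO-305 anchor would add nothing.

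Flag events starting after release in the AE listing, so that recalled out-of-clinic events can be told apart. The flag also helps with the omeprazole-alone column, where a completer's attribution window is (18 − 15) × 24 = 72 h and an early leaver's could now be longer.

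The cost is a short amendment and a wider reporting rule at an existing call. The downside is a few recalled unrelated events from outside confinement. If the study is too far advanced to amend, show early leavers' post-dose observation time beside the TEAE tables.

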3.2. Discussion of Study Design

Overall

The study is designed to determine the dosing conditions which might affect the PK profile of LOXO-305 in healthy adult subjects.

The effect of food will be thus assessed by measuring the change in the PK of LOXO-305 after dosing under fed conditions (with a standard breakfast) versus fasting condition. This study will support assessment of early phase drug combinations of FDA-approved products with LOXO-305 as part of the ongoing clinical trial, LOXO-BTK-18001. For approved products, administration will follow specifications of the United States product insert, which may specify administration with "food", not specifically a "high fat meal". A "standard meal" is considered more consistent with the food conditions identified in the package insert of the approved products that will be assessed in combination with LOXO-305. In consideration of the diet which the patient population LOXO-305 is intended to treat (patients with previously treated CLL/SLL, WM, MCL, MZL, and other B-cell NHL) normally consume, a standard

breakfast has been chosen as the meal with which to administer LOXO-305 under fed conditions (Treatment B).⁶

The aqueous solubility of LOXO-305 is similar across the range of pH in the GI track (e.g. CCI Loxo Oncology Inc., data on file) and therefore there is unlikely to be an effect of GI pH modification on the solubility and subsequent oral absorption of LOXO-305 from the GI tract. However, LOXO-305 is formulated with excipients that cause release of LOXO-305 from the formulation to be somewhat slower under acidic conditions than neutral conditions, and the clinical impact of this slower dissolution is unknown. The effect of reduced stomach acidity on the PK of LOXO-305 will be tested in this study by raising the gastric pH with omeprazole, a PPI.

A PPI was selected over other antacids drugs because this drug class is considered to suppress gastric acid secretion to a greater extent and for a longer duration than some other gastric pH-elevating agents, such as H₂ blockers and antacids.

Subjects will be randomized to treatment sequences to minimize assignment bias. The 2 treatment sequences will be ABC and BAC. Subjects will be randomly assigned to 1 of the 2 treatment sequences, according to the randomization scheme issued by Covance. A crossover design is used to reduce the residual variability as every subject acts as their own control. The washout period of 7 days between LOXO-305 doses in Treatments A and B and the washout period of 7 days between the doses of LOXO-305 administered in Treatments A or B and the first dose of omeprazole in Treatment C is considered sufficient to prevent carryover effects of the treatments.

Conducting the study in healthy adult subjects mitigates the potential confounding effects of the disease state and concomitant medications.

